**TRIAL SUMMARY**

Abbreviated Title	Effect of liraglutide on neural responses to HFCS in individuals with obesity
Trial Phase	2A
Indication	Healthy lean (n=15) and obese individuals (n=30)
Control	N/A
Product	Liraglutide
Number of Subjects	45
Estimated Enrollment Period	24 months
Aims	Aim 1 – To investigate the effect of 12-16-week intervention with GLP-1 analogue (liraglutide 3.0mg) on eating behavior and food craving in individuals with obesity (age 15-39 yrs) who chronically consume SSBs ( $\geq$ 5 SSBs/week).
Inclusion Criteria	
 
1. 15-39 years old
 
2. Lean (BMI 18.5-24.9 kg/m^2) with normoglycemia with fasting plasma glucose (FPG) <100 mg/dL, 2-hour post oral glucose tolerance test (75gm glucose) glucose level <140 mg/dL and glycosylated hemoglobin (HbA1c) <5.7% or
 
3. Obese (BMI 30-45 kg/m^2) with or without prediabetes (insulin resistance) but without diabetes <200 mg/dL,
 
4. Ingest <math>\geq</math>5 sugar sweetened beverages per week,
 
5. Weight stable for at least 6 months,
 
6. Able to provide written and verbal informed consent,
 
7. Able to read and write in English Able to read and write in English,
 

Exclusion Criteria	
 
1. Current active participation in a weight loss program or weight loss of <math>\geq</math>10% of total body weight during the previous 6 months,
 
2. Prior bariatric surgery or current gastric balloon,
 
3. Following a vegetarian/vegan diet or dieting/restricting food due to significant food allergies, including but not limited to lactose intolerance and celiac disease,
 
4. Significant medical condition such as cardiac or pulmonary disease, coagulopathy, gastrointestinal disorder, known history of Type 1 or T2D, current psychiatric disorders (including suicidal ideation and depression), including eating disorders (DSM-IV criteria), neurological injury or illness
 
5. Current use of weight-loss medications or supplements, psychiatric medications or anti-hyperglycemic medications (stable dose of metformin for <math>\geq</math> 6 months is acceptable),
 
6. History of or family history of multiple endocrine neoplasia type 2 (MEN-II) or medullary thyroid cancer, alcoholism, or previous history of pancreatitis,
 
7. Females who are pregnant or lactating, or who are unwilling to use proper contraception or remain abstinent,
 

Treatment Plan	Eligible obese subjects will self-administer Liraglutide once daily for 12-16 weeks.

## STUDY SCHEMA

## LIST OF ABBREVIATIONS

AE – adverse event  
FDA – Food and Drug Administration  
fMRI – functional magnetic resonance imaging  
HbA1c – hemoglobin A1c  
HFCS – high fructose corn syrup  
GLP-1 – Glucagon-like peptide 1  
PFC – pre frontal cortex  
PI – principal investigator  
RCT – randomized controlled trial  
SAE – serious adverse event  
SSB – Sugar sweetened beverage  
T2D – Type 2 Diabetes  
YCCI – Yale Center for Clinical Investigation

## RATIONALE AND BACKGROUND

Obesity and overweight has reached epidemic proportions in America with the current prevalence rate of 35% in adolescents. This is particularly alarming since over 20% of obese adolescents develop prediabetes and the majority of obese adolescents will be obese in adulthood predisposing them to a myriad of diseases such as type 2 diabetes (T2D). In parallel with the obesity epidemic, added-sugar consumption has markedly increased in Western diets, and is postulated to be a contributor to this public health crisis. Notably, adolescents are the highest consumers of added sugar, with ~20% of their caloric intake accounted for by sugar and nearly half of those calories from sugar-sweetened beverages (SSBs) which contain high fructose corn syrup (HFCS). Evidence indicates that increased consumption of sugars such as HFCS found in SSBs is associated with future weight gain. Therefore, understanding the physiologic mechanisms modulating brain reward responses that may promote excess sugar consumption may provide insight into novel interventions to quell SSB ingestion, thus attenuating obesity in adolescents.

Indeed, excessive sugar intake is highly rewarding in the brain. In recent studies, we have found that simple sugars such as glucose and fructose affect brain pathways implicated in regulation of appetite and reward. Specifically, glucose stimulates homeostatic (hypothalamic) brain regions and fructose stimulates hedonic (striatal) regions and both require activation of the prefrontal cortex (PFC), which exerts regulatory control over impulses, choices, and decision-making, to regulate these brain regions to control food intake. We previously reported that obese adolescents have decreased medial PFC (mPFC) control responses to consumption of glucose and fructose, suggesting diminished capacity to down-regulate hedonic (striatal) and homeostatic (hypothalamic) brain responses that may affect eating behavior. Furthermore, we found hyperactivation of reward (striatal) responses to fructose ingestion in obese adolescents. Notably, these two highly rewarding simple sugars are rarely, if ever, consumed in isolation, but rather are ingested in combination forms such as HFCS. Thus, the question arises: what interventions may attenuate excess sugar (SSB) consumption in obese adolescents by potentially decreasing the neural reward response to HFCS.

Increased ingestion of added sugars, such as HFCS in SSBs is associated with the obesity epidemic, long- term weight gain, T2D, and cardiovascular disease (CVD). Furthermore, ingestion of SSB's may contribute to the development of T2D and CVD independent of obesity. Notably, adolescents are the highest consumers of added-sugars, thus studying this vulnerable population to elucidate novel therapeutic strategies to prevent the development of T2D is vital. It is striking that adolescents with obesity and prediabetes (insulin resistance) progress to develop T2D much more rapidly than adults with prediabetes, within 21 months vs. 5 years, respectively. Additionally, once adolescents develop obesity and T2D they often are not successful in maintaining glycemic control with lifestyle and metformin therapy or losing weight with lifestyle interventions, and subsequently their glycemic control deteriorates necessitating more aggressive pharmacological treatment such as insulin therapy. It is clear that prevention of T2D in adolescents is imperative and interventions to mitigate SSB consumption, halt weight gain, and progression to T2D are critical. Yet, therapies to decrease added-sugar consumption, weight gain, and progression to T2D in adolescents are blatantly lacking. GLP-1 analogues improve glycemic control, contribute to weight loss, and may attenuate food preference for sweets. Thus, it is important to elucidate how GLP-1 analogues effect neural responses in reward-motivation pathways of the brain to affect food preference and contribute to weight loss in obese prediabetic adolescents. The expected results may significantly contribute to our understanding of neural mechanisms involved in GLP-1 analogue action to affect food preference and curb excess sugar intake in the setting of adolescent obesity and prediabetes and have important implications for clinical practice in the

care of obese prediabetic adolescents to prevent progression to T2D.

### **Rationale for Trial and Selected Patients**

Adolescents are the highest consumers of SSB potentially because their developing brains are most susceptible to the rewarding neural effects of sugar consumption. The prefrontal cortex (PFC) (implicated in control of impulses, choices, and decision-making) is not fully developed in adolescents, undergoing significant development into young adulthood, and thus has not yet gained mature regulatory capacity over reward-motivation (striatal) and hunger-satiety (hypothalamic) brain regions, to control SSB intake and potentially mitigate excessive consumption in adolescents. Thus, we specifically target this vulnerable population (adolescents) to understand neural mechanisms involved in excess sugar consumption which predisposes to the development of obesity, prediabetes, and T2D.

As the original target study population is adolescents, we are now expanding the age group to include 15-17 year olds; we are basing this on several new studies which have been conducted recently and published, as well as the FDA approval of liraglutide for children age 10-17 who have type 2 diabetes. As of June 2019, liraglutide is now FDA approved for treatment of type 2 diabetes in children 10 years and older. Liraglutide has been FDA approved for treatment of obesity in adults >18 years old since 2014, and was approved in December, 2020 for the treatment of obesity in adolescents aged 12-17 years; additionally, several clinical trials have been conducted in children and adolescents (age 7-17 years old) with obesity alone without type 2 diabetes to assess safety, tolerability and dose. Liraglutide has been shown to have a similar safety, tolerability and pharmacokinetic profile in younger children (age 7-11 years) with obesity as in adults. In a safety and tolerability trial, liraglutide was found to have a similar profile in terms of side effects and pharmacokinetics as in adults with obesity and adolescents with obesity (age 12-17 years) at the same dose used for weight management in adults. Earlier in 2020, a clinical trial entitled “Effect of Liraglutide for Weight Management in Pubertal Adolescent Subjects With Obesity: 56-week Double-blind, Randomised, Parallel-group, Placebo-controlled, Multi-national Trial Followed by 26-week Period Off Study-drug” was completed, published, and liraglutide 3.0mg is now FDA-approved for treatment of adolescents (age 12-17 years old) with obesity, without diabetes. Given that liraglutide has been shown to have a similar safety profile in adolescents with obesity as adults with obesity, we believe it would be beneficial to lower the study’s age minimum to mid-late adolescents (age 15-17) to better understand the neural mechanisms in adolescents with excess sugar consumption. Indeed, adolescents are the highest consumers of added sugar and sugar sweetened beverages and the population we are most interested in both for understanding underlying mechanisms which lead to or quell SSB consumption as well as treatment for this high risk population.

The neural mechanisms involved in the reward response to “real-life” sugars, such as HFCS, may provide insight into novel interventions to quell SSB ingestion. Excessive sugar intake is highly rewarding in the brain. Glucose stimulates homeostatic (hypothalamic) brain regions and fructose stimulates hedonic(striatal) regions and both require the prefrontal cortex (PFC) to regulate these brain region’s responses to control food intake. In preliminary work, we found that obese adolescents have decreased medial PFC (mPFC) executive control response to ingestion of glucose and fructose, suggesting diminished capacity to down-regulate hedonic (striatal) and homeostatic (hypothalamic) brain regions that may affect eating behavior. Furthermore, we found hyperactivation of reward (striatal) response to fructose ingestion in obese adolescents. This is important because fructose in combination with

glucose makes up “real-life” sugar in forms such as HFCS found in SSBs, but the impact of “real-life” sugar ingestion on neural responses in adolescents is not known. Thus, we chose to investigate brain response to ingestion of HFCS (60% fructose/40% glucose) as it is contained in the five most commonly consumed SSBs in the United States, including Pepsi, Coke, [name], Mountain Dew, and Sprite.

Therapies to mitigate added-sugar consumption, weight gain, and progression to T2D in adolescents are blatantly lacking. GLP-1 analogues decreased food intake and potentially affect food preference away from sugar-containing food. We will elucidate neural mechanisms by which the GLP-1 analogue liraglutide tempers food intake and potentially alters food preference. Importantly, GLP-1 analogues may prove to be a novel intervention to curb excess sugar consumption by shifting preference away from beverages containing sugar and, thus, contribute to prevention of T2D.

## STATEMENT OF PURPOSE/OBJECTIVES

**Aim 1** – To investigate the effect of GLP-1 analogue (liraglutide 3.0mg) on eating behavior and food craving in individuals with obesity (age 15-39 yrs) who chronically consume SSBs ( $\geq 5$  SSBs/week).

**Exploratory Aim:** To investigate the role of specific metabolic/hormonal responses (serum leptin, insulin, glucose, GLP-1, acyl-ghrelin) induced by food consumption, and in the setting of liraglutide treatment

## PHARMACEUTICAL AND THERAPEUTIC BACKGROUND

### Product Description & Rationale for Use

Liraglutide was approved for use in adults by the FDA in 2010 for T2D treatment and in 2014 for obesity treatment. It is a glucagon-like peptide-1 (GLP-1) receptor agonist indicated as an adjunct to a reduced-calorie diet and increased physical activity for chronic weight management in adult patients with an initial body mass index (BMI) of 30 kg/m^2 or greater (obese) or 27 kg/m^2 or greater (overweight) in the presence of at least one weight-related comorbid condition (e.g. hypertension, type 2 diabetes mellitus, or dyslipidemia). Liraglutide, a GLP-1 analogue produced by Novo Nordisk used in the treatment of both obesity and T2D, contributes to weight loss and improves glycosylated hemoglobin levels.

It is an intriguing therapeutic intervention to potentially affect food preference and decrease sugar consumption and attenuate weight gain. Liraglutide is an analogue of an incretin hormone, glucagon-like peptide-1 (GLP-1), which is secreted by L cells in of the small intestine in response to food ingestion. GLP-1 dysregulation is noted in individuals with obesity and T2D with decreased GLP-1 levels post-prandially. Of particular interest is how GLP-1 analogues, such as liraglutide, decrease food intake, and alter food preference.

Preclinical studies have demonstrated that liraglutide not only decreases food intake but also changes food preference. Rats offered chow and candy, obtained 75% of their calories from candy and gained 15- 20% more weight than chow feed counterparts; subsequently with 12-16 weeks of liraglutide treatment the rats decreased their food intake and reversed food preference with an increase in chow intake and decrease in candy ingestion. In another study, rats treated with a GLP-1 analogue no longer preferred the environment which contained chocolate pellets in a conditioned place preference test. Furthermore, in a mouse model, GLP-1 was released from taste-bud cells in response to sweet compounds and GLP-1 receptor knockout mice demonstrated decreased taste response to sweeteners and reduced behavioral response to sweet compounds (short-term lick test) compared to wild-type mice. These studies suggest that GLP-1 is important in sweet taste sensitivity and that GLP-1 analogues may shift food preference away from sugar-containing foods.

### Pharmacokinetics

**Absorption** - Following subcutaneous administration, maximum concentrations of liraglutide are achieved at 11 hours post dosing. The average liraglutide steady state concentration (AUC0-24) reached approximately 116 ng/mL in obese (BMI 30-45 kg/m^2) subjects following administration of Saxenda®. Liraglutide exposure increased proportionally in the dose range of 0.6 mg to 3 mg. The intra-subject coefficient of variation for liraglutide AUC was 11% following single dose administration. Liraglutide exposures were considered similar among three subcutaneous

injection sites (upper arm, abdomen, and thigh). Absolute bioavailability of liraglutide following subcutaneous administration is approximately 55%.

**Distribution** - The mean apparent volume of distribution after subcutaneous administration of liraglutide 3 mg is 20-25 L (for a person weighing approximately 100 kg). The mean volume of distribution after intravenous administration of liraglutide is 0.07 L/kg. Liraglutide is extensively bound to plasma protein (greater than 98%).

**Metabolism** - During the initial 24 hours following administration of a single [3H]-liraglutide dose to healthy subjects, the major component in plasma was intact liraglutide. Liraglutide is endogenously metabolized in a similar manner to large proteins without a specific organ as a major route of elimination.

**Elimination** - Following a [3H]-liraglutide dose, intact liraglutide was not detected in urine or feces. Only a minor part of the administered radioactivity was excreted as liraglutide-related metabolites in urine or feces (6% and 5%, respectively). The majority of urine and feces radioactivity was excreted during the first 6-8 days. The mean apparent clearance following subcutaneous administration of a single dose of liraglutide is approximately 0.9-1.4 L/h with an elimination half-life of approximately 13 hours, making liraglutide suitable for once daily administration.

### **Drug Interactions**

Liraglutide has low potential for pharmacokinetic drug-drug interactions related to cytochrome P450 (CYP) and plasma protein binding.

### **Drug Supply and Dose**

Liraglutide will be supplied in the following package sizes containing disposable, pre-filled, multi-dose pens. Each individual pen delivers doses of 0.6 mg, 1.2 mg, 1.8 mg, 2.4 mg or 3 mg (6 mg/mL, 3 mL). The study drug will be purchased from Novo Nordisk.

3 x Saxenda® pen NDC 0169-2800-13  
5 x Saxenda® pen NDC 0169-2800-15

Each Saxenda® pen is for use by a single patient. A Saxenda® pen should never be shared between patients, even if the needle is changed.

To minimize side effects; liraglutide will be titrated over the first month: starting at a dose of 0.6mg daily for 7 days, increasing to 1.2mg on day 8 for the next 7 days, increasing to 1.8mg on day 15 for the next 7 days, increasing to 2.4mg on day 22 for the next 7 days, and then increasing to 3.0mg on day 39 and continuing this dose for the remainder of the study (12-16 weeks total). If a subject is not able to increase dose to 3.0mg, they will be maintained on the highest dose they are able to tolerate, at a minimum of 1.2mg. If a subject is not able to tolerate the medication at all or at a dose of at least 1.2mg, the medication will be discontinued and the subject will not continue in the study.

### **Storage and Stability and Handling Requirements**

Prior to first use, Saxenda® should be stored in a refrigerator between 36°F to 46°F (2°C to 8°C)

Prior to first use	After first use	
Refrigerated 36°F to 46°F (2°C to 8°C)	Room Temperature 59°F to 86°F (15°C to 30°C)	Refrigerated 36°F to 46°F (2°C to 8°C)
Until expiration date	30 days	

It should not be stored in the freezer or directly adjacent to the refrigerator cooling element. Do not freeze Saxenda® and do not use Saxenda® if it has been frozen.

After initial use of the Saxenda® pen, the pen can be stored for 30 days at controlled room temperature (59°F to 86°F; 15°C to 30°C) or in a refrigerator (36°F to 46°F; 2°C to 8°C). Keep the pen cap on when not in use. Saxenda® should be protected from excessive heat and sunlight. Always remove and safely discard the needle after each injection and store the Saxenda® pen without an injection needle attached. This will reduce the potential for contamination, infection, and leakage while also ensuring dosing accuracy.

### **Contraindications**

Personal or family history of medullary thyroid carcinoma or Multiple Endocrine Neoplasia syndrome type 2, Hypersensitivity to liraglutide or any product components and Pregnancy.

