### Exclusion Criteria

1. Current active participation in a weight loss program or weight loss of >=10% of total body weight during the previous 6 months
2. Prior bariatric surgery or current gastric balloon
3. Following a vegetarian/vegan diet or dieting/restricting food due to significant food allergies, including but not limited to lactose intolerance and celiac disease
4. Significant medical condition such as cardiac or pulmonary disease, coagulopathy, gastrointestinal disorder, known history of Type 1 or Type 2 diabetes, current psychiatric disorders (including suicidal ideation and depression), current eating disorders (DSM-IV criteria), neurological injury or illness
5. Current use of weight-loss medications or supplements, psychiatric medications or anti-hyperglycemic medications (stable dose of metformin for > 6 months is acceptable)
6. History of or family history of multiple endocrine neoplasia type 2 (MEN-II) or medullary

thyroid cancer, alcoholism, or previous history of pancreatitis

7. Females who are pregnant or lactating, or who are unwilling to use proper contraception or remain abstinent,

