### Discontinuing Liraglutide

If a subject is not able to tolerate the medication at all due to persistent vomiting or intolerable nausea, the medication will be discontinued and the subject will not continue in the study. If the subject's mood changes while participating in the study, as assessed by PHQ-9, the PI will contact the subject and assess whether they need intervention and determine if they can continue in the study or if the drug should be discontinued.

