## **Holding the Dose**

Liraglutide will be stopped temporarily if ANY the following occur:

- Persistent vomiting or nausea
- Moderate-severe dehydration (as a result of nausea/vomiting)
- Significant persistent abdominal pain
- Other side effects which the participant attributes to starting study drug

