## **Restarting the Dose**

- If participant is amenable to trying the study drug again, the medication will be restarted within 4 days with phone call follow up to assess tolerability. If participant is not able to tolerate the study drug on re-initiation then they will not continue in the study. If the participant does not want to participate in the study at any time point, they may withdraw from the study.
- If the participant withdraws from the study at any point, they will be asked to complete the end of study questionnaires, dietary recalls and to return for a final weight, body composition measurement and end-of-study blood work. If the participants complete these visits, they will be compensated the same as if these visits had been completed at the end of the study.

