#### **Duration of Therapy**

For Obese patients, Liraglutide will be administered daily for 12-16 weeks. If any of the following occur, the medication will be stopped:

- Pancreatitis (severe abdominal pain, increased amylase/lipase)
- Severe dehydration
- The participant chooses not to continue in the study

Lean controls will not be given study drug.

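### Hypersensitivity to liraglutide is a contraindication but neither an exclusion nor a bar to restarting drug, and the main safety-lab section omits the week 4 and 8 labs and pregnancy tests required under Minimizing Risks

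*Combined protocol and SAP*

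**What the plan says.** **Contraindications.** The section names three: a personal or family history of medullary thyroid carcinoma or MEN 2, and then "Hypersensitivity to liraglutide or any product components and Pregnancy". Warnings and Precautions lists hypersensitivity reactions again.

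**Eligibility.** Exclusion 6 begins "History of or family history of multiple endocrine neoplasia type 2 (MEN-II) or medullary" and, in the Trial Summary, ends with "alcoholism, or previous history of pancreatitis". Exclusion 7 covers "Females who are pregnant or lactating, or who are unwilling to use proper contraception or remain abstinent". Neither copy of the list mentions drug hypersensitivity.

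**Rules on treatment.**
- Discontinuing Liraglutide deals with a participant who cannot take the drug for gastrointestinal reasons ("If a subject is not able to tolerate the medication at all due to persistent vomiting or intolerable nausea") and with mood change on the PHQ-9.
- Holding the Dose names vomiting or nausea, dehydration and abdominal pain, and ends with a general item: "Other side effects which the participant attributes to starting study drug".
- Restarting the Dose says: "If participant is amenable to trying the study drug again, the medication will be restarted within 4 days". A phone call follows. A participant who fails on re-exposure leaves the study.
- Duration of Therapy gives the stop list, introduced by "If any of the following occur, the medication will be stopped". Its three items are pancreatitis, severe dehydration and the participant's choice.

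**Safety labs and pregnancy test.** Safety Laboratory Procedures and Assessments places them at week 0 and week 12-16 and describes weeks 4 and 8 as phone sessions with the PHQ-9. The liraglutide paragraph of Minimizing Risks places both labs and pregnancy test at weeks 4, 8 and 12-16, and says that the labs check renal, pancreatic, liver and thyroid function.

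**The concern.** Staff screen from the eligibility criteria and manage side effects from the hold, restart and stop rules. On hypersensitivity, neither set reflects the contraindication stated elsewhere in the same protocol. A person with a past reaction to the drug could be enrolled and dosed. A person with a suspected reaction on study could be given the drug again within days, on the sole written condition of being willing. The participants are aged 15 to 39.

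Pregnancy is handled at entry, but no action is written for a positive test during treatment. The timing of that test also depends on which section is read. If it is done only at the end of dosing, it can no longer limit exposure to a drug that the protocol says is contraindicated in pregnancy.

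**Working it through.** The plan gives no figure to reproduce here. The check is a side-by-side reading with simple counts.

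**1. Contraindications against exclusions**

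| Contraindication | Matching exclusion |
|---|---|
| Medullary thyroid carcinoma / MEN 2 | Item 6 |
| Pregnancy | Item 7 |
| Hypersensitivity to liraglutide or a component | None |

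Two nearby items do not fill the gap. Item 3 mentions allergy, but only food allergy that restricts the diet. Item 5 excludes current use of weight-loss drugs and most glucose-lowering drugs, not a past reaction to one.

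**2. A suspected hypersensitivity reaction on treatment**

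- Discontinuing Liraglutide: not named.
- Duration of Therapy: not named.
- Holding the Dose: reached only through the general item, which stops drug temporarily.
- Restarting the Dose: drug resumes within 4 days if the participant agrees. No clinician assessment is required and no type of reaction is excepted. For mood change, by contrast, the protocol does write in the PI's judgement.

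**3. A positive pregnancy test on treatment**

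None of the discontinuation, hold or stop rules names it. The restart rule is not relevant, because it follows a hold for side effects.

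**4. The two lab and pregnancy-test schedules**

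| | Safety Laboratory Procedures | Minimizing Risks |
|---|---|---|
| Week 0 | Yes | Screening labs before start |
| Week 4 | Phone session, PHQ-9 | Labs and pregnancy test |
| Week 8 | Phone session, PHQ-9 | Labs and pregnancy test |
| Week 12-16 | Yes | Yes |
| On-treatment time points | 1 | 3 |

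The OGTT section adds a pregnancy test at baseline.

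**5. Daily doses before the first on-treatment pregnancy test**

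Assumptions: one dose a day, none held, and the test at the end of the named week. Doses = weeks × 7.

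- Safety Laboratory Procedures: 12 × 7 = 84 to 16 × 7 = 112.
- Minimizing Risks: 4 × 7 = 28.
- Difference: 84 − 28 = 56 to 112 − 28 = 84 doses.

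A test early in the named week lowers each count by up to 7. These counts measure timing, not harm.

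**6. Panel**

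Creatinine/GFR is in the screening list, and week 0 refers back to that list. The list that follows for the scheduled safety labs (amylase, lipase, AST, ALT, calcitonin, urine pregnancy test) does not name it, while Minimizing Risks says that renal function is monitored. Whether it is measured on treatment is therefore unclear.

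**The case against.** The best case for the plan is that its other safeguards would prevent harm. The contraindication and the warning stand in the same protocol. Weekly calls with a study physician or nurse practitioner look for adverse effects. The PI holds authority for patient safety, and an independent monitor assists with continuation decisions. Eligibility is decided from a checklist that is not reproduced here and might contain the item. For pregnancy, contraception or abstinence is required at entry, and the Contraindications section makes the right action plain. All of this lowers the risk. None of it changes a restart rule that, as written, permits re-exposure.

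Four stronger readings are tempting, and the documents do not support them.

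- A reader might infer that the two schedules are incompatible. They are not. Neither says that its time points are the only ones, a phone session does not rule out a blood draw, and testing at weeks 0, 4, 8 and 12-16 satisfies both. One section omits two time points that the other requires.
- A reader might infer that renal function is never measured under the main safety-lab section. Creatinine/GFR is named at screening. Only the on-treatment panel is unclear.
- A reader might infer that, without interim amylase and lipase, the pancreatitis stop rule cannot work. That rule describes a clinical event with severe pain. Persistent abdominal pain already triggers a hold, and nothing bars a lipase test for cause.
- A reader might infer that a pregnant participant could be restarted within 4 days. The hold and restart route is triggered by side effects and does not apply to pregnancy.

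The cell marks in the Appendix 1 flow chart are not readable in this copy, and the Appendix 3 visit sheet is not included. Either may show which schedule was intended. The mismatch in the running text would remain.

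**Conclusion.** The point holds as a patient-safety inconsistency that should be fixed. One of three stated contraindications is missing from the exclusions. A suspected hypersensitivity reaction leads to a temporary hold and a restart within 4 days, with no exception. No stop rule names such a reaction or a positive on-treatment pregnancy test. The main safety-lab section leaves out the week 4 and week 8 time points required under Minimizing Risks. A site following it would do the first on-treatment pregnancy test at about the end of dosing, some 56 to 84 doses later than under the other section.

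The scale is small. At most the 30 dosed participants with obesity are affected, and for pregnancy only the females among them, from 0 to 30 because no sex split is given. The documents give no hypersensitivity rate, so no expected number of events is offered. No sample size, error rate or analysis changes. The dose counts rest on daily dosing without holds and on tests at the end of the named week.

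**What to change.** 1. **Exclusions (Trial Summary and Exclusion Criteria).** Add known hypersensitivity to liraglutide or to any component of the product, for participants who will be dosed.
2. **Duration of Therapy and Restarting the Dose.** Add to the stop list a suspected hypersensitivity reaction, in the study clinician's judgement, and a confirmed pregnancy. State in the restart rule that drug is not resumed after a suspected hypersensitivity reaction.
3. **Safety Laboratory Procedures and Assessments.** Bring the section into line with Minimizing Risks: safety labs and urine pregnancy test at weeks 0, 4, 8 and 12-16. Align Appendix 1, and say whether creatinine/GFR is in the on-treatment panel.

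**Cost.** The text changes are one exclusion line, two stop-list lines, one no-restart sentence and one reconciled schedule. The effect on recruitment should be small. The interim testing comes to at most two contacts per dosed participant, 30 × 2 = 60 in all, which Minimizing Risks already calls for. The week 8 contact can coincide with the planned second CGM placement. Week 4 needs a short visit if bloods are drawn.
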